In 2019, the global age-standardized suicide rate was 9.0 per 100,000 population, and in Brazil, the suicide rate was 6.7 per 100,000 inhabitants (World Health Organization, 2021). In 2021, a significant majority of suicides - 73% - occurred in low-and-middle-income countries (LMICs) (World Health Organization, n.d). This data explains the urgent need for effective suicide prevention strategies in LMICs, including Brazil, where suicide is a growing public health concern. Despite the Brazilian rate being inferior to the global age-standardized rate in 2019, other alarming data highlight the urgency of addressing this public health issue in Brazil. Regardless of the 36% global reduction in the numbers of suicides from 2000 to 2019 (Damiano et al., 2024), some countries, such as Brazil, still face the challenge to address rising numbers. The Americas region has demonstrated a 17% increase in the same period, and Brazil figures as one of the countries with the most significant rise (43%) (World Health Organization, 2021). According to the most recent epidemiological bulletin released by the Brazilian government, from 2000 to 2021, there was a 42% increase in the suicide mortality rate, from 5.2 to 7.5 per

100,000 inhabitants (Brasil, Ministério da Saúde, Secretaria de Vigilância em Saúde e Ambiente, 2024).

Brief Cognitive Behavioral Therapy

CBT for suicide prevention protocols are designed to help high-risk individuals to identify patient-specific factors that trigger and intensify suicidal thoughts and behaviors, as well as to develop effective coping strategies when dealing with stressors and problems that activate the suicidal mode (Mann et al., 2021; Bryan & Rudd, 2018).

In BCBT, to reach those goals, treatment is composed of three main phases, as follows: Emotional Regulation and Crisis Management, Targeting Belief Systems Related to Suicide and Relapse Prevention (Bryan & Rudd, 2018). See table 1 in Supplementary Material. The first phase focuses on developing effective strategies for regulating intense emotions and managing crises in a manner that is adaptive (Bryan & Rudd, 2018). During this stage, the objective is to help the patient identify emotional triggers and learn mindfulness techniques to promote assertive responses to stressful situations. The development of an individualized action plan to address critical moments with greater emotional control is considered to be essential for therapeutic progress (Bryan & Rudd, 2018).

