The second phase centers on identifying and modifying the negative and distorted thought patterns that underlie suicidal ideation. Through cognitive restructuring, the goal is to cultivate a more realistic and adaptive view of oneself and the future, while enhancing emotional resilience. Addressing belief systems related to suicide is a critical component of the therapeutic process, as these beliefs are often linked to suicidal behavior (Bryan & Rudd, 2018).

The final phase emphasizes relapse prevention, focusing on identifying risk factors that may trigger the return of suicidal thoughts. Personalized preventive strategies will be developed, including strengthening social support networks, continuous practice of coping skills, and creating a detailed contingency plan to handle potential future adversities. The aim is to equip the patient with robust tools to maintain mental

health and well-being in the long term, thereby reducing the likelihood of recurrent suicidal crises (Bryan et al., 2024).

Supportive psychotherapy

Concerning control treatment characteristics in suicidology, approximately 60% of the Randomized Controlled Trials across nearly 50 years of research had their active treatment condition compared to active control conditions, such as psychotherapy suicidality (Fox et al., 2020); however, the chosen psychotherapy approach as a comparator was not specified in this analysis.

There has been a historical debate between researchers and clinicians about the understanding of what makes psychotherapy work. This debate could be summarized in the conflict existing among two main groups: those who believe that the therapy's efficacy depends solely on the common factors, and the other group that defends the insertion of the specific factors (Wampold, 2015).

Common factors refer to the elements that can be found in various psychotherapeutic approaches and are believed to contribute to the effectiveness of therapy, regardless of the specific techniques derived from their philosophical and conceptual basis. These factors include elements such as the therapeutic alliance, empathy, positive regard, and the client's expectations of therapy, among others (Norcross & Lambert, 2011).

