Concurrent pharmacotherapy will not be restricted during trial participation, as withholding medication in this high-risk outpatient sample would be ethically untenable. All psychotropic medications, doses, and any changes will be systematically recorded at each assessment visit. Medication use will be reported descriptively and included as a covariate in pre-specified sensitivity analyses to assess its potential confounding influence on the primary outcome. Additional individual psychotherapy outside of the study arms is not permitted during the active treatment phase (weeks 1–12); if clinically necessary, the occurrence will be documented as a protocol deviation and handled under the intention-to-treat principle. Group psychoeducation, crisis-line contacts, and emergency psychiatric interventions are permitted and will be recorded as secondary clinical outcomes and adverse events.

Outcomes

The primary outcome is suicide attempt, evaluated longitudinally to determine the efficacy of BCBT in reducing suicidal behavior. Secondary outcomes include suicidal ideation, self-directed violence, depressive symptoms, anxiety, meaning in life, subjective well-being, religiosity, quality of life, hypomanic symptoms, sleep disturbance, fatigue, and suicide-specific cognitions.

Instruments

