- Multiplicity: The primary outcome (time-to-first suicide attempt) is the sole pre-specified confirmatory endpoint, tested at two-sided $\alpha=0.05$. Secondary outcomes are organized in the following interpretive hierarchy: (1) suicidal ideation (BSI, C-SSRS ideation subscale); (2) non-suicidal self-injury (DSHI-s); (3) depressive symptoms (BDI-II); (4) anxiety (GAD-7); (5) treatment feasibility and acceptability. No formal α -adjustment is planned across secondary outcomes; results should be interpreted in light of the number of comparisons made and regarded as exploratory. Exploratory moderator and mediator analyses carry no inferential weight regarding treatment efficacy and will be clearly labelled as hypothesis-generating throughout the manuscript.

Data capture and management

REDCap with role-based access, audit trails, range checks, and encrypted storage. Identifiers stored separately; audio files on secure institutional servers. Only authorized personnel access identifiable data.

Monitoring and safety

Independent Data and Safety Monitoring Board (DSMB) reviews SAEs quarterly (or ad hoc) and may recommend protocol modifications or early termination for safety. AEs/SAEs reported to CEP/CONEP per Brazilian regulation. Participants receive 24/7 emergency contacts.

Discussion

The BCBT-BR trial rigorously evaluates whether suicide-specific CBT confers advantages over common-factor ST in a Brazilian outpatient setting. Strengths include an active comparator, blinded assessment, event-focused primary outcome, therapist cross-training with fidelity checks, and cultural adaptation. Findings will guide scalable implementation of suicide-focused care in LMIC public mental health systems.

Ethics and Registration

Ethics: CONEP/Plataforma Brasil approval CAAE 88755725.9.0000.0068

Registration: ClinicalTrials.gov [registration pending; CAAE 88755725.9.0000.0068 refers to the Brazilian ethics approval (CONEP/Plataforma Brasil) and is reported separately above] 88755725.9.0000.0068

Protocol amendments: Any substantial changes will be submitted to ethics committees and updated in registries.

Funding

There is no funding for this trial. RFD receives scholarship from São Paulo Research Foundation (FAPESP) (#2024/10058-0).

Author Contributions

- Conceptualization: [name] (LB), [name] (RFD), [name] (ECM), [name] (CB)
- Methodology: LB, [name] (RERF), CB, RFD

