
Supplementary Material

Table 1: The structure and components of BCBT (Bryan & Rudd, 2018)

Phase	1	2	3
Sessions	1-5	6-10	11-12
Therapeutic component	Emotional Regulation and Crisis Management	Targeting Belief Systems Related to Suicide	Relapse Prevention
Techniques	Crisis Response Plan; Means restriction counseling; Sleep stimulus control; Relaxation skills training; Mindfulness skills training; Reasons for living list; Survival kitk.	ABC Worksheet ; Challenging Questions Worksheet; Problematic Patterns of Thinking Worksheet; Activity planning; Coping cards.	Relapse prevention task.

Table 2: Assessment schedule

Schedule of Assessments (CONSORT format)

Measure	T0	T1	T2	T3	T4	T5	T6	T7	T8	T9	T10	T11	T12	T13	T14	T15
Sociodemographic	X															
Treatment History	X															
Weekly Follow-up		X	X	X	X	X	X	X	X	X	X	X	X	X	X	X
BSI	X	X	X	X	X	X	X	X	X	X	X	X	X	X	X	X
BDI-II	X	X	X	X	X	X	X	X	X	X	X	X	X	X	X	X
DUREL	X	X	X	X	X	X	X	X	X	X	X	X	X	X	X	X
GAD-7	X	X	X	X	X	X	X	X	X	X	X	X	X	X	X	X
PHQ-9	X	X	X	X	X	X	X	X	X	X	X	X	X	X	X	X
PIL	X	X	X	X	X	X	X	X	X	X	X	X	X	X	X	X
SHS	X	X	X	X	X	X	X	X	X	X	X	X	X	X	X	X
SF-12	X	X	X	X	X	X	X	X	X	X	X	X	X	X	X	X
HCL-32	X	X	X	X	X	X	X	X	X	X	X	X	X	X	X	X
PROMIS Sleep	X	X	X	X	X	X	X	X	X	X	X	X	X	X	X	X
MADRS		X	X	X	X	X	X	X	X	X	X	X	X	X	X	X
C-SSRS		X	X	X	X	X	X	X	X	X	X	X	X	X	X	X
NIH BFI		X	X	X	X	X	X	X	X	X	X	X	X	X	X	X
FSS		X	X	X	X	X	X	X	X	X	X	X	X	X	X	X
SCS-R	X	X	X	X	X	X	X	X	X	X	X	X	X	X	X	X
SAFER	X	X	X	X	X	X	X	X	X	X	X	X	X	X	X	X
SAFER Follow-Up														X	X	X

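### Attending a permitted psychoeducation group or calling a crisis line is recorded as an adverse event in itself, which puts non-harm into the harms counts

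*Protocol*

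**What the plan says.** The Concomitant Treatments section of the protocol names three kinds of outside help and gives all three the same treatment: "Group psychoeducation, crisis-line contacts, and emergency psychiatric interventions are permitted and will be recorded as secondary clinical outcomes and adverse events". It does not say which service takes which label, and it does not require a clinical event behind the contact. No other section of the protocol defines an adverse event in a way that would narrow the sentence.

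Three other places bear on where these records go and who may generate them:

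- **Trial Design** commits the report to CONSORT 2025 with its harms extension.
- **Monitoring and safety** has the DSMB review serious adverse events each quarter and sends adverse and serious adverse events to CEP/CONEP. It adds, with no limit to one arm: "Participants receive 24/7 emergency contacts".
- **Supplementary Table 1** lists among the BCBT techniques of sessions 1 to 5: "Crisis Response Plan; Means restriction counseling; Sleep stimulus control". It names neither crisis lines nor psychoeducation groups.

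**The concern.** An adverse event is meant to capture something untoward that happened to the participant. Going to a psychoeducation group is use of a service that the protocol allows. A call to a crisis line may follow a deterioration, or it may be a sensible use of help with no deterioration at all. The sentence makes the contact itself the event, so the two cases cannot be told apart in the data.

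What is at stake is the harms reporting. Adverse-event counts in both arms would mix harm with ordinary service use, and so would the reports to the ethics bodies. If the arms use these services to different extents for any reason, the table by arm would show a difference that is not a difference in harm. The second label, secondary clinical outcome, adds to the difficulty: for a crisis-line contact the protocol does not say whether more is better or worse.

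**Working it through.** The protocol states no adverse-event rate and no contact rate, so there is no figure of the plan's own to reproduce. The check is first one of text, then an illustration of mechanism with assumed inputs.

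**1. Text.** The Concomitant Treatments sentence covers three services and attaches two labels to them. For emergency psychiatric interventions a safety label is reasonable, since such an intervention can mark a real safety event. For group psychoeducation no untoward occurrence is implied. For crisis-line contacts one may or may not be present. Nothing elsewhere in the protocol restricts the rule, so, read plainly, service use alone triggers an adverse-event record.

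**2. Could use differ by arm, and which way?**

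- Reason to expect more crisis-line use under BCBT: a "Crisis Response Plan" is a named BCBT technique, and the account of phase 1 in the Introduction says: "The development of an individualized action plan to address critical moments with greater emotional control is considered to be essential for therapeutic progress". This makes a difference plausible but does not state one. It has no bearing on psychoeducation groups.
- Reason to expect less: under Hypotheses, BCBT is expected to do better than ST on suicide-related outcomes. Fewer crises could mean fewer contacts.
- Reason to expect no difference: the 24/7 contacts are not restricted to one arm.

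The protocol does not settle the sign.

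**3. Illustration.** Let *t* be the true adverse-event risk, equal in both arms, and *h* the share of participants with at least one contact counted as an adverse event, taken as independent of *t*.

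- Apparent risk in an arm = 1 - (1 - *t*)(1 - *h*)
- Spurious arm difference, BCBT minus ST = (1 - *t*)(*h*_BCBT - *h*_ST)

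The arm size of 75 is from the protocol abstract. All rates are assumptions. With *t* = 20% and *h*_ST = 20%, the ST arm shows 1 - 0.80 × 0.80 = 36%, or 27 of 75. The BCBT arm shows:

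| Assumed BCBT contact | Apparent BCBT risk | Participants of 75 | Spurious difference |
|---|---|---|---|
| 10% | 1 - 0.80 × 0.90 = 28% | 21 | -8 points |
| 20% | 1 - 0.80 × 0.80 = 36% | 27 | 0 |
| 30% | 1 - 0.80 × 0.70 = 44% | 33 | +8 points |
| 40% | 1 - 0.80 × 0.60 = 52% | 39 | +16 points |

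Letting *t* run from 10% to 30% with the same contact rates, the extremes both occur at *t* = 10%: 0.90 × (0.10 - 0.20) = -9 points and 0.90 × (0.40 - 0.20) = +18 points.

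In every row both arms show more than the true 20%, including the row with no arm difference. If the contacts are not counted as adverse events, the spurious difference is zero in every row.

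**The case against.** The strongest case on the other side has five parts.

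- **The sentence can be read distributively**, with some items as outcomes and others, such as emergency interventions, as adverse events. That reading is possible, but the sentence does not say which item belongs where, so staff could code the same contact differently. The wording still needs correction.
- **A reader might infer a bias against BCBT**, because BCBT teaches crisis planning and its success would then be counted as harm. The protocol does not support this. No section says that BCBT promotes crisis-line use or psychoeducation groups, the emergency contacts are not limited to one arm, and the sign reverses if BCBT reduces crises. A risk ratio such as 1.5 (30% against 20%) would also need assumed contact rates and no other adverse events at all. With a 20% true risk, the same contact rates give 44% against 36%, a ratio of about 1.2.
- **A reader might also see a contradiction with the outcome lists**, since none of the three services is in the list under Outcomes or in the hierarchy under Multiplicity. This is weak. The list opens "Secondary outcomes include suicidal ideation, self-directed violence, depressive symptoms, anxiety, meaning in life", so it need not be complete, and the section on the measurement battery expressly keeps several measures outside the hierarchy.
- **No formal safety comparison is specified.** The protocol describes no between-arm test of adverse events, the DSMB reviews serious events, and events might be tabulated by type, where a reader could see what each one is. This stands, and it limits the consequence to descriptive reporting.
- **Over-recording is a defensible caution in a high-risk sample, and replacing a mechanical rule with judgement has its own risk.** For emergency psychiatric interventions this is persuasive, and the fix leaves them alone. For the other two services the risk is that unblinded staff classify differently by arm, which is why the classification should sit with a blinded assessor.

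**Conclusion.** The defect is in a rule that the protocol states, and is not a detail left to a later document. As written, use of two permitted services counts as an adverse event with no untoward occurrence behind it. This inflates the adverse-event counts in both arms, and it could shift the descriptive harms table in either direction if use differs by arm. The illustrated range of -9 to +18 points rests wholly on assumed contact rates, an assumed true risk and independence between the two. It shows the mechanism and is not an estimate for this trial.

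Severity is minor. The effect is confined to descriptive harms reporting and the reports to the ethics bodies. The time-to-first-attempt analysis does not use these records.

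**What to change.** Reword the sentence under Concomitant Treatments to say the following:

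- Group psychoeducation and crisis-line contacts are recorded by arm as health-service use and reported descriptively as exploratory.
- An adverse or serious adverse event is recorded only when the clinical event behind the contact meets the trial's adverse-event definition. The definition is applied identically in both arms by the blinded assessor who already makes the weekly safety calls (section on ascertainment and adjudication).
- Emergency psychiatric interventions remain recorded as safety events and are shown by type.

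This changes how contacts are classified and nothing about what is permitted; all three services stay available as now.

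The cost is one sentence and a split of the REDCap form into service use and adverse events. The downside is that the event behind each contact has to be classified instead of being coded automatically. It is best done before data collection, because contacts coded automatically as adverse events are hard to reclassify later.

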Brief Cognitive-Behavioral Therapy for Suicide Prevention in a Brazilian Outpatient Sample (BCBT-BR): Protocol for a Two-Arm Randomized Controlled Trial

Short title: BCBT-BR Trial Protocol

Date: May 4th, 2026

Abstract

Importance: Suicide remains a leading cause of premature mortality worldwide. While global rates have declined since 2000, the Region of the Americas shows concerning increases, particularly in Brazil. Brief Cognitive-Behavioral Therapy (BCBT) has demonstrated efficacy in reducing suicide attempts in high-income countries, but evidence from low- and middle-income countries (LMICs) and civilian outpatient settings remains limited.

Objective: To evaluate whether BCBT reduces suicide attempt incidence over 6 months compared with manualized Supportive Psychotherapy (ST) among high-risk Brazilian adults receiving university outpatient care.

Design, Setting, and Participants: Single-site, parallel-group, superiority randomized clinical trial (RCT) at the Institute of Psychiatry, University of São Paulo, Brazil. Adults aged 18-65 years with current suicidal ideation and/or suicide attempt within the past month will be randomized 1:1 to receive 12 weekly 60-minute sessions of BCBT or dose-matched ST (N=150; 75/group).

Interventions: BCBT targeting emotion regulation and cognitive reappraisal versus manualized ST providing emotional support without systematic skills training.

Main Outcomes and Measures: Primary outcome is time-to-first suicide attempt over 6 months, assessed by blinded evaluators. Secondary outcomes include suicidal ideation, non-suicidal self-injury, depression, anxiety, treatment feasibility and acceptability. Assessments occur at baseline, mid-treatment (week 6), end-of-treatment (week 12), and 3- and 6-month follow-ups, with weekly attempt surveillance. Intention-to-treat analyses will employ Cox proportional hazards regression (primary outcome) and mixed-effects/generalized linear models (secondary outcomes). Sample size provides 80% power to detect HR=0.50 ($\alpha=0.05$, 25% attrition).

Conclusions and Relevance: This trial will provide critical evidence on BCBT effectiveness in LMIC outpatient settings, informing scalable suicide prevention strategies.

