Secondary objectives: Compare trajectories of suicidal ideation, NSSI, depression, and anxiety; evaluate feasibility/acceptability; explore predictors and moderators of response (e.g., prior attempts, sex, age, symptom severity).

Hypotheses

1. BCBT will yield a lower hazard of suicide attempt (superiority).

2. BCBT and ST will show similar improvements in general anxiety/depression, but BCBT will outperform ST on suicide-related outcomes.
3. BCBT will demonstrate high feasibility and acceptability in this population, as reflected by satisfactory recruitment rates, session attendance, treatment adherence, and positive patient satisfaction ratings.
4. Baseline characteristics, including history of prior suicide attempts, baseline symptom severity, age, and sex, will be associated with differential clinical outcomes over follow-up.

Methods

Trial Design

Single-site, parallel-group, superiority RCT (1:1) with blinded outcome assessment and 6-month follow-up. The protocol follows the SPIRIT 2025 guidelines; reporting will follow the CONSORT 2025 guidelines and the extensions for non-pharmacological interventions and harms.

Randomization

Participants will be randomly assigned in a 1:1 ratio, stratified by sex and prior suicide attempt, using a computer-generated permuted-block randomization sequence with variable block sizes (blocks of 4 and 6) to prevent allocation prediction. The sequence will be generated by an independent researcher with no involvement in participant recruitment or outcome assessment, using validated statistical software. Participants will be enrolled by the study coordinator; treatment allocation will be released only after eligibility is formally confirmed and informed consent is obtained. Allocation concealment will be maintained through a centralized, web-based randomization module within REDCap, which withholds the assigned arm until the enrollment step is completed and locked. Neither the enrolling clinician nor the participant will have access to forthcoming allocations.

Blinding

Given the nature of psychotherapy research, blinding of participants and therapists to treatment allocation is not feasible (Cuijpers et al., 2015). However, all outcome

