ranked secondary analyses; the PHQ-9 provides a brief screening complement and the MADRS a clinician-rated perspective sensitive to change. Similarly, the NIH-BFI offers a multi-dimensional clinician-rated fatigue assessment, while the FSS captures subjective functional impairment. Instruments measuring religiosity (DUREL), quality of life (SF-12), hypomanic symptoms (HCL-32), sleep (PROMIS), meaning in life (PIL), and subjective well-being (SHS) are included for descriptive and exploratory purposes and are not part of the ranked secondary outcome hierarchy. Assessment burden was considered during protocol development; instruments are administered in a fixed, piloted order, and estimated completion time per assessment visit does not exceed 60 minutes.

Sample size and power

We power the primary analysis (time-to-first attempt) using Schoenfeld's method for Cox models [32]. Assuming a hazard ratio (HR) = 0.50 (BCBT vs ST), two-sided $\alpha=0.05$, and 80% power, the number of required events is:

$$E=[\ln(HR)]^2(Z_{1-\alpha/2}+Z_{1-\beta})^2$$

If the overall 6-month event rate is ~15% in this high-risk sample (e.g., 20% ST vs 10% BCBT), then $N \approx 113$ would be required to accrue ~17 events. To accommodate 25% attrition, we plan $N=150$ (75 per group), yielding $\geq 80\%$ power under these assumptions. This sample also provides $\geq 80\%$ power to detect small-to-moderate between-group effects (e.g., standardized mean difference $d \approx 0.38$) on continuous secondary outcomes with repeated measures.

Statistical analysis plan

- Principles: Intention-to-treat primary; $\alpha=0.05$, two-sided; 95% CIs. Time zero is defined as the date of randomization. Follow-up begins at randomization and continues until first suicide attempt, death, withdrawal of consent, or administrative censoring at the 6-month assessment, whichever occurs first. Any suicide attempt occurring after eligibility screening but before

randomization will be documented as a baseline clinical event but will not count as a primary outcome event; this ensures that the risk period is aligned comparably across both arms from the moment of allocation.

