- Primary analysis: Cox model estimating HR for BCBT vs ST, adjusting for stratification factors (sex, prior suicide attempt), with additional covariates (age and baseline suicidal ideation) included in sensitivity analyses. Check proportional hazards (Schoenfeld residuals); if violated, use time-varying effects or restricted mean survival time. Given approximately 17 anticipated events, including four covariates yields an events-per-variable (EPV) ratio of ~4, below the commonly recommended threshold of 10. To reduce the risk of overfitting, the pre-specified primary model will include only the two stratification factors (sex and prior suicide attempt) as covariates (EPV ~8.5). Adjustment for age and baseline suicidal ideation will be conducted as a supplementary sensitivity analysis.
- Secondary analyses: Linear mixed-effects models (random intercepts) for fixed effects: time, group, group×time; GEE/logistic models for binary outcomes (e.g., any NSSI).
- Missing data: Missing At Random (MAR) is defined as missingness that depends only on observed data; Missing Not At Random (MNAR) refers to missingness that depends on unobserved data (e.g., patients drop out because their suicidal ideation worsened). Time-to-event outcome: participants lost to follow-up will be censored at the date of last confirmed contact. Sensitivity analyses will include: (a) best-case scenario—all BCBT dropouts are assumed attempt-free (censored at day 180) while all ST dropouts are assumed to have attempted at their last contact date; (b)

worst-case scenario—the reverse; (c) tipping-point analysis—identifying the minimum assumed increase in hazard for censored BCBT participants that renders the primary result non-significant.

- Exploratory moderators (hypothesis-generating only): These analyses are explicitly exploratory. Given the projected sample size and anticipated number of primary events, treatment-by-baseline interaction tests are underpowered for definitive subgroup inference and must not be interpreted as confirmatory evidence of effect heterogeneity. Interactions of treatment with baseline factors (e.g., prior attempt, sex, age, baseline symptom severity) will be examined with marginal effects and graphical probes. Mediation (e.g., change in cognitive distortions) may be explored descriptively if data allow. All findings will be framed as generating hypotheses for future adequately powered trials.

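### The required event count leaves out the factor of 4 for 1:1 allocation: HR 0.50 needs 66 events, not about 17, so N=150 has roughly 30–38% power, not 80%

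*Protocol*

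**What the plan says.** The section Sample size and power states: "We power the primary analysis (time-to-first attempt) using Schoenfeld's method for Cox models". Its inputs are HR 0.50 for BCBT against ST, two-sided alpha 0.05 and 80% power. The formula as printed has no term for the allocation ratio. With an overall 6-month event rate of about 15% (20% ST, 10% BCBT given as an example), the section says that about 113 participants "would be required to accrue ~17 events". It then allows for 25% attrition, arrives at N=150 (75 per group) and claims at least 80% power.

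The Abstract (Main Outcomes and Measures) repeats the claim: "Sample size provides 80% power to detect HR=0.50". The Randomization section fixes the allocation: "Participants will be randomly assigned in a 1:1 ratio". The Primary analysis item of the statistical analysis plan section uses the same number as a forecast when it limits the covariates: "Given approximately 17 anticipated events".

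**The concern.** Seventeen events is very few for detecting a halving of the hazard with 80% power in a 1:1 trial. The number matches Schoenfeld's expression with the allocation term left out, which makes it too small by a factor of 4. N≈113, N=150 and the power claim all follow from it.

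The Multiplicity item makes time to first suicide attempt the only confirmatory endpoint, so the trial's main conclusion depends on this calculation. If BCBT truly halves the hazard, the trial as sized would miss it about two times in three. A reader told that power was 80% could then take a non-significant result as evidence against BCBT. The ethics committee and the DSMB also rely on the stated figure.

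**Working it through.** **Inputs (all from the protocol).** HR 0.50; two-sided alpha 0.05, z = 1.960; 80% power, z = 0.842; 1:1 allocation, so p(1−p) = 1/4; overall event rate 15%; attrition 25%; N=150.

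**Reproducing the protocol's figures.**
- (1.960 + 0.842)² = 7.849 and (ln 0.5)² = 0.4805.
- 7.849 / 0.4805 = 16.34, rounded up to 17.
- 17 / 0.15 = 113, and 113 / 0.75 = 151, close to the planned 150.

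The whole chain is recovered, but only without the allocation term.

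**Correct Schoenfeld count.** E = (z-sum)² / [p(1−p)(ln HR)²] = 4 × 7.849 / 0.4805 = 65.3, so 66 events.

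**Could another standard method give 17?** Freedman's formula gives 71. A one-sided 0.05 test gives 52 (Schoenfeld) or 56 (Freedman). None comes close.

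**Events expected with N=150.**
- Dropouts contribute no events: 150 × 0.75 × 0.15 = 16.9, about 17.
- Dropout spread over follow-up (exponential, 25% by 6 months, 20%/10% rates): about 19.6.
- No events lost: 150 × 0.15 = 22.5.

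**Power and detectable effect.** Power = Φ(0.6931 × √E / 2 − 1.960). HR detectable with 80% power = exp(−2 × 2.8016 / √E). Largest observed HR reaching p<0.05 = exp(−2 × 1.960 / √E).

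| Events | Power at HR 0.50 | HR detectable with 80% power | Observed HR needed for p<0.05 |
|---|---|---|---|
| 17 | 29.8% | 0.26 | 0.39 |
| 19.6 | 33.6% | – | – |
| 22.5 | 37.6% | 0.31 | 0.44 |

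An observed HR of exactly 0.50 would have a 95% CI of 0.5 × exp(±1.960 × 2 / √17) = 0.19 to 1.29 with 17 events. With 22.5 events the upper limit is still 1.14.

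**Cross-checks.**
- A log-rank simulation (75 per arm, 20% control risk, HR 0.50) gave 29% power with all attrition at baseline, 32% with attrition spread over follow-up and 36% with none.
- A comparison of proportions, 20% against 10%, has 40% power with 75 per arm and needs 199 per arm for 80%.

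**What 66 events would take.** 66 / 0.15 = 440 participants with no events lost. With the protocol's own inflation, 440 / 0.75 = 587. With dropout spread over follow-up, 66 × 150 / 19.6 is about 505. Keeping N=150 would require an event rate of 66 / 150 = 44%, or 66 / 112.5 = 59% among completers.

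**The case against.** The printed formula multiplies where it should divide (read literally it gives 3.8), and this may be a fault of text extraction. That is a fair caution, but the finding does not depend on the print. It rests on the number 17, which the protocol carries into both sample sizes.

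Four further points refine the finding without removing it:

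- **The forecast in the Primary analysis item is sound.** It speaks of anticipated events, not required ones, and 112.5 × 0.15 = 16.9 is a fair expectation for N=150. The events-per-variable figures there need no change while N stays at 150.
- **The example rates are not exactly HR 0.50.** Under proportional hazards, 20% and 10% imply ln(0.9) / ln(0.8) = 0.47. At that HR, 56 events are needed and power is 34% (17 events) to 43% (22.5 events). This is still about half the stated power.
- **587 is the upper end of a range.** The protocol censors dropouts at last confirmed contact, so they contribute time and possibly events. The need lies between 440 and 587, depending on when they leave.
- **A low chance of success is not none.** An observed HR of 0.50 would not reach significance, but a true HR of 0.50 would still do so in about 30–38% of trials.

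The protocol already commits to reporting a hazard ratio with 95% CIs. It calls its interaction tests underpowered, but nowhere says this of the primary test.

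**Conclusion.** The error is real and must be fixed. The required number of events is understated fourfold (17 instead of 66), and the claim of 80% power for HR 0.50 is wrong in both the Abstract and the sample size section. At the stated HR, N=150 gives about 30% to 38% power, or at most about 43% if the example rates are read as HR 0.47. These figures assume the protocol's 15% event rate and proportional hazards. The range reflects how many events attrition removes, and no treatment of attrition brings power near 80%.

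**What to change.** - In Sample size and power, correct the formula to E = 4(Z for 1−α/2 + Z for 1−β)² / (ln HR)² and the result to 66 events. Remove the statement that about 113 participants suffice.
- There and in the Abstract, replace the 80% claim with what N=150 provides if the event rate is about 15%: some 30–38% power for HR 0.50, and a detectable HR of about 0.26–0.31 at 80% power. State the attrition assumption behind each end of the range.
- State which effect is assumed, HR 0.50 or the 20%/10% rates (HR 0.47), so that the inputs agree.
- In the Primary analysis item, keep the forecast of about 17 events, but make clear that it is not the number that gives 80% power.
- Record a decision by the sponsor and the ethics committee on whether to keep N=150 for a confirmatory superiority test or to change the design. If N=150 stays, it would help to state in advance that a non-significant primary result is inconclusive.

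If N is kept, the cost is protocol wording and an ethics and registry update, with no change to conduct. The protocol lists trial registration as pending, so the correction could precede the confirmed record. Meeting the original power target would mean about three to four times as many participants (440 / 150 = 2.9; 587 / 150 = 3.9).
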